#### Selected Baseline characteristics

1. Age, BMI, education, co-morbidity, risk markers, co-medication

#### Risk in adolescence

- 1. Selected baseline characteristics in adolescence
- 2. Anemia (primary outcome) in adolescence
- 3. Depression (primary outcome) in adolescence

 Bipolar disorders and schizoaffective disorders are excluded. This specification was added on request of the Safety Monitoring and Advisory Council.

Supporting document SOP BMT 01.09 – Doc 5002.02 – Effective date 21.03.2017

#### Risk of long-term use

- 1. Selected baseline characteristics in long-term user
- 2. Anemia (primary outcome) in long-term user
- 3. Depression (primary outcome) in long-term user
- 4. SAEs in long-term user

#### 5.4.5 Definition of other safety outcomes

#### SAEs

SAEs are defined as any adverse event that results in death, a life-threatening experience, inpatient hospitalization, persistent or significant disability/incapacity, or requires medical/surgical intervention to prevent one of the said outcomes. The following items were shown in detail:

- 1. VTE/ATE
- 2. Death
- 3. SAEs by organ system
- 4. Malignant neoplasms
- 5. Malformation of the newborn child

#### 5.4.6 Definition of other outcomes of interest

#### Surgery because of endometriosis symptoms

#### Is defined as:

- 1. Diagnostic surgical intervention
- 2. Any therapeutic surgery related to endometriosis

#### 5.5 Missing data

The investigators were instructed to obtain complete information on primary and secondary outcome variables and primary risk factors. In case of missing data, numbers will be presented in the respective table categories in the descriptive analysis. However, for certain variables (e.g. Mood Score), the last value is carried forward to replace missing items and calculate the related score (as defined in Appendix IV).

Women with multiple exposure or unspecific treatment will be specified as "Allocation unknown".

#### 6. **Data Handling**

Two different databases are used for data collection: the administrative database (ADB) for physician and study participant details and the study database (SDB) for all questionnaire data (baseline and all subsequent follow-ups as well as data gathered during validation of self-reported events).

For each interim analysis and for the final analysis the database is frozen at a predefined time point. The database will be 'cleaned' within 4 weeks of the database freeze. After the final freeze approximately 4 months after the last follow-up questionnaires have been sent to the study participants), no additional incoming data is entered in the database – this database will represent

Supporting document SOP BMT 01.09 – Doc 5002.02 – Effective date 21.03.2017

the final data source for all analyses. Safety copies are made of each database so that all calculations can be repeated if necessary.

#### 6.1 Data coding

Disease diagnoses are coded using the  $ICD10^{12}$  (International Classification of Diseases). Additional codes are used for the coding of events that are of specific interest.

Concomitant medication is coded using WHO ATC-Codes. Surgical procedures are coded using the modified operation and procedure coding list (OPS) provided by DIMDI (German Institute for Medical Documentation and Information). All other relevant information will be coded by a ZEG specific, highly standardized coding system (ZEG Coding Dictionary). All outcomes of interest are additionally described in a case narrative, the "case summary".

#### 6.2 Variable definitions

All time-related variables (age, first diagnosis, first symptoms) are calculated in relation to the study entry date.

#### 6.2.1 Definition of derived variables

The definition of derived or calculated variables from observed items for display in the analysis tables will be described in Appendix IV.

#### 6.2.2 Definition of subgroups

Variable label	Definition
Country	Germany vs. Poland vs. Hungary vs. Switzerland vs. Russia vs. Ukraine
Long-term user	15 months or more of continuous EMT intake
EMT user type	Starter vs. restarter vs. switcher
Diagnosis classification	Diagnosis of endometriosis confirmed via surgery / laparoscopy vs. diagnosis based on clinical symptoms
Age categories	< 20 vs. 20 to < 30 vs. 30 to < 40 vs. >= 40
Age-standardization	Referenced population: NAED cohort

12 ICD10-Codes Version 2009

13 ATC-Codes Version 2010

14 OPS-Codes Version 2009

Supporting document SOP BMT 01.09 – Doc 5002.02 – Effective date 21.03.2017

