1. INTRODUCTION

Endometriosis is a common, chronic, gynecological disease characterized by pain and impaired fertility. Prevalence estimates vary widely, however, the proportion of premenopausal women living with endometriosis is thought to be approximately 10% [1]. Endometriosis causes chronic inflammation, ovarian cyst formation, fibrosis and adhesions [1]. There seems to be little correlation between the extent of the disease and severity of pain experienced [2]. However, symptoms seem to respond to decreased circulating estrogen [3] and the mainstay of medical treatment is hormonal induced anovulation and a reduction in endogenous estrogen production.

While currently approved medications for endometriosis have proven to be effective in decreasing pelvic pain, many have clinically relevant side-effects. Danazol, a testosterone analogue, can cause androgenization and GnRH agonists are known to decrease bone mineral density. Consequently, treatment for endometriosis with these medications needs to be stopped after 6-12 months. Post-treatment endometrial lesions tend to regenerate, with many women's symptoms reoccurring 1-2 months after the cessation of treatment. Some countries in Europe also allow the use of progestogens for the treatment of endometriosis, however, there is currently no pharmaceutical preparation licensed for the treatment of endometriosis in all member states of the European Union.³

Dienogest (DNG) is a 19-nortestosterone derivative progestogen that is highly selective for progesterone receptors [4]. DNG has been available as part of a low-dose combined oral contraceptive containing 2mg of dienogest and 30µg of ethinylestradiol (DNG/EE) in Germany since 1995. As a progestin in DNG/EE, DNG is known for having strong endometrial effects that improve dysmenorrhoea and decrease the duration of menstrual bleeding [5]. In addition, progestogens may also modulate pain associated with endometriosis by dampening neuronal activity [3]. As a monotherapy for the treatment of endometriosis DNG 2mg/day has been available in Japan since 2008. In Japan it has been found to be a reliable and effective treatment for dysmenorrhea, premenstrual pain, dyspareunia and diffuse pelvic pain associated with endometriosis associated pelvic pain with improved tolerability compared with 3.75mg leuprolide acetate (LA) [7-8]. Unlike LA, DNG has minimal effects on bone density and may offer women a new option for the long-term control of endometriosis symptoms.

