#### **Abbreviations**

ADB	Administrative Database
ADR	Adverse Drug Reaction
AT	As Treated
ATE	Arterial Thromboembolism
ATC	Anatomical Therapeutic Chemical Classification System
СНС	Combined Hormonal Contraceptives
CI	Confidence Interval
DIMDI	German Institute for Medical Documentation and Information
EMT	Endometriosis treatment
EURAS	EURopean Active Surveillance (study)
FU	Follow-up
GP	General Practitioner
НСР	Health Care Professional
HR	Hazard Ratio
ICD-10	International Classification of Diseases, 10th revision
IP	Incidence Proportion
IR	Incidence Rate
IRR	Incidence Rate Ratio
ITT	Intention to Treat
LOCF	Last observation carrying forward
NAED	Not approved hormonal medications for the treatment of endometriosis
OAED	Other approved hormonal medications for the treatment of endometriosis
OR	Odds Ratio
Р	Prevalence
SAE	Serious Adverse Event
SAP	Statistical Analysis Plan
SDB	Study Database
SMAC	Safety Monitoring and Advisory Council
VTE	Venous Thromboembolism
WHO	World Health Organization
WY	Women years
ZEG	Berlin Center for Epidemiology & Health Research (acronym for the German term 'Zentrum für Epidemiologie & Gesundheitsforschung Berlin')

Supporting document SOP BMT 01.09 - Doc 5002.02 - Effective date 21.03.2017

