#### 5.1 Analysis sets

There are no specific inclusion or exclusion criteria. However, women with a language barrier, a non-hormonal or not newly prescribed baseline medication or women who are pregnant at study enrollment will be excluded from the analysis. The final analyses will include both an "as treated" (AT) and an "intention-to-treat" (ITT) analysis. All women who are not excluded from the analysis will be assigned to the ITT and AT population at baseline. Only women with follow up information will be considered for longitudinal analysis (e.g. distribution of outcomes over time, incidence rates, regression). Women who never started their prescribed baseline medication will be considered in the ITT analysis, but excluded from the AT analysis. The safety conclusions of the study will be based on the AT analysis.

Supporting document SOP BMT 01.09 – Doc 5002.02 – Effective date 21.03.2017

This study follows three cohorts: users of Visanne (DNG), users of other medication approved for the treatment of endometriosis (OAED) and users of non-approved hormonal medications prescribed for endometriosis treatment or those approved only in some participating countries (NAED).

Distribution of women, population characteristics (baseline and follow up) as well as clinical outcomes will be presented for the following cohorts and sub-categories.

Cohort Sub-category for presentation	
DNG	Complete cohort
OAED	GnRH-a, Danazol, complete cohort
NAED	Combined hormonal contraceptives, other progestins, complete

The cohorts consist of new users (starter and restarter) or switcher of a hormonal endometriosis treatment. For the primary analysis, outcomes of interest or adverse events will be assigned to the treatment at the time the outcome or the event occurred. Women with multiple exposure or unspecific treatment will be specified as "Allocation unknown". Women who stopped their treatment will be assigned to an "Ex-use" cohort.

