#### Section B-7 Distribution and selected baseline characteristics of Visanne long-term user

#### Section B-7.1 Duration of Visanne use

Table B-7.1.1 Duration of Visanne use

	DNG long-term user*
Number (%) of women	xx ( 100%)
Duration of DNG use	
15 months to < 24 months	xx ( xx.x%)
24 months to < 30 months	xx ( xx.x%)
30 months to < 36 months	xx ( xx.x%)
36 months to < 42 months	xx ( xx.x%)
42 months to < 48 months	xx ( xx.x%)
48 months to < 54 months	xx ( xx.x%)
54 months to < 60 months	xx ( xx.x%)
60 months to < 66 months	xx ( xx.x%)
66 months to < 72 months	xx ( xx.x%)
72 months to < 78 months	xx ( xx.x%)
78 months to < 84 months	xx ( xx.x%)
84 months and more	xx ( xx.x%)

Note: \*Long-term: defined as continuous use for >= 15 months. They may have started with other than DNG treatment.

Table B-7.1.2	Duration of Visanne use, Starter
Table B-7.1.3	Duration of Visanne use, Switcher
Table B-7.1.4	Duration of Visanne use, Restarter
Table B-7.1.5	Duration of Visanne use, Diagnosis confirmed by surgery
Table B-7.1.6	Duration of Visanne use, Diagnosis based on clinical symptoms
Table B-7.1.7	Duration of Visanne use, Germany
Table B-7.1.8	Duration of Visanne use, Poland
Table B-7.1.9	Duration of Visanne use, Hungary
Table B-7.1.10	Duration of Visanne use, Switzerland
Table B-7.1.11	Duration of Visanne use, Russia
Table B-7.1.12	Duration of Visanne use. Ukraine

Supporting document SOP BMT 01.09 – Doc 5002.02 – Effective date 21.03.2017

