#### Section C-3.4 Incidence rate of serious adverse events by organ system for long-term use

Table C-3.4.1 Incidence rate of serious adverse events by organ system for long-term use, AT population, Complete cohort

	DNG		OAED			NAED		Ex-use	Allocation unknown	Total
		GnRH-a	Danazol	All OAED	СНС	Other progestin	All NAED			
Number of women years*	XX	xx								
Serious adverse events**	xx	xx								
IR (95% CI) Thereof***	xx.x (xx.x-x.x)	xx.x (xx.x-x.x)	xx.x (xx.x–x.x)	xx.x (xx.x–x.x)	xx.x (xx.x-x.x)	xx.x (xx.x–x.x)	xx.x (xx.x–x.x)	xx.x (xx.x–x.x)	xx.x (xx.x-x.x)	xx.x (xx.x–x.x)
Infectious diseases	XX		XX	XX	XX		XX	XX	XX	XX
Neoplasms, malignant	xx	xx	xx.x (xx.x–x.x)	xx	XX	XX	xx.x (xx.x–x.x)	xx.x (xx.x–x.x)	xx	xx
Neoplasms, benign	xx	xx	xx.x (xx.x–x.x)	xx	xx		xx	xx.x (xx.x–x.x)	xx.x (xx.x–x.x)	xx
Diseases of the blood	xx.x (xx.x–x.x)	,	xx.x (xx.x–x.x)	xx.x (xx.x–x.x) xx	xx.x (xx.x–x.x)	xx.x (xx.x–x.x)	xx.x (xx.x–x.x)	xx.x (xx.x–x.x) xx	xx.x (xx.x–x.x) xx	xx.x (xx.x–x.x)
and blood-forming organs Endocrine diseases	xx.x (xx.x–x.x)		xx.x (xx.x–x.x)	xx.x (xx.x-x.x)	xx.x (xx.x–x.x)					
	xx.x (xx.x-x.x)	xx.x (xx.x–x.x)	xx.x (xx.x-x.x)	xx.x (xx.x-x.x)	xx.x (xx.x-x.x)					
Psychiatric and neurological disorders	xx xx.x (xx.x-x.x)	xx xx.x (xx.x–x.x)	xx xx.x (xx.x–x.x)	xx xx.x (xx.x–x.x)	xx xx.x (xx.x-x.x)		xx xx.x (xx.x–x.x)	xx xx.x (xx.x–x.x)	xx xx.x (xx.x–x.x)	xx.x (xx.x–x.x)
Eye	xx xx.x (xx.x-x.x)		xx xx.x (xx.x–x.x)	xx.x (xx.x-x.x)						
Ear	xx xx.x (xx.x–x.x)	xx.x (xx.x–x.x)								
Cardiovascular system	xx	xx	xx xx.x (xx.x–x.x)	xx	xx	, ,	xx	xx xx.x (xx.x–x.x)	xx	xx
Respiratory system	xx	xx	xx (xx.x-x.x)	xx	XX	xx	xx xx.x (xx.x-x.x)	xx xx.x (xx.x–x.x)	xx	xx

Supporting document SOP BMT 01.09 - Doc 5002.02 - Effective date 21.03.2017

Digestive system	xx			
	xx.x (xx.x-x.x)			
Skin	XX			
	xx.x (xx.x-x.x)			
Musculoskeletal system	xx			
and connective tissue	xx.x (xx.x-x.x)			
Genitourinary system	xx			
	xx.x (xx.x-x.x)			
Pregnancy, delivery and	xx			
Puerperium	xx.x (xx.x-x.x)			
Injury, poisoning,	xx			
accidents etc.	xx.x (xx.x-x.x)	xx.x (xx.x-x.x)	xx.x (xx.x–x.x)	xx.x (xx.x-x.x)

Note: \* Only women with 15 months or more of continuous EMT intake were considered. Incidence rates are calculated based on an observation time of 15 months or more

Note: \*\* Incidence rate is shown per 104 women years.

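### The SAP's long-term user definition is not tied to the drug in the table column, so recent switchers to DNG can enter the DNG long-term outcome tables, while the DNG baseline table implies 15 months on DNG itself

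*SAP*

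**What the plan says.** SAP 6.2.2 (Definition of subgroups) gives the only general definition of a long-term user: "15 months or more of continuous EMT intake". The abbreviation list expands EMT as "Endometriosis treatment". No drug or cohort is named.

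The note to Table C-3.4.1 (SAEs in long-term use) applies the same wording: "Only women with 15 months or more of continuous EMT intake were considered". That table reports by DNG, OAED, NAED and Ex-use. Tables C-2.5 to C-2.7 (anemia, depression and discontinuation in long-term use) are given by title only, so 6.2.2 is the only definition they have.

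For the primary analysis, SAP 5.1 states that "outcomes of interest or adverse events will be assigned to the treatment at the time the outcome or the event occurred".

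The DNG long-term user tables in Section B-7 read differently. The note to Table B-7.1.1 says: "Long-term: defined as continuous use for >= 15 months. They may have started with other than DNG treatment". The table sorts all DNG long-term users by duration of DNG use, and its lowest category is "15 months to < 24 months". There is no lower row and no row for missing duration.

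SAP 5.4.4 lists anemia, depression and SAEs in long-term users among the secondary outcomes.

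**The concern.** Two steps decide who appears in a long-term DNG column: qualifying as long-term, and being allocated to DNG. Read literally, 6.2.2 makes the first step on any endometriosis treatment and 5.1 makes the second on the treatment of the moment. Nothing in the outcome tables then sets a minimum time on DNG.

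The long-term DNG rates would mix sustained DNG exposure with new DNG exposure in previously treated women. A late effect could be diluted, and an early effect could be reported as a long-term one. SAP 1.1 gives the unknown influence of DNG over a longer period as part of the rationale, and SAP section 4 expects most women to stop or change regimen during the study, so switching is not a marginal case. The baseline tables in B-7 and the outcome tables in C-2.5 to C-2.7 and C-3.4 could also describe different women under the same name.

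**Working it through.** The plan gives no figure that depends on this definition, so there is nothing to reproduce. The check is to put the rules side by side and follow example women through them.

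**Inputs.** Qualification: 15 months of continuous EMT (SAP 6.2.2; note to Table C-3.4.1). Allocation of events: current treatment (SAP 5.1). Duration of DNG use: rows from 15 months upward (Table B-7.1.1). Neither woman has a break of 4 weeks, the gap used to define a restarter in SAP section 3.

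| Step | 12 months GnRH agonist, then 3 months DNG | 14 months GnRH agonist, then 1 month DNG |
|---|---|---|
| Total EMT | 12 + 3 = 15 months | 14 + 1 = 15 months |
| Long-term under 6.2.2, read literally | yes | yes |
| Column for an event on DNG (5.1) | DNG | DNG |
| DNG duration for Table B-7.1.1 | 3 months | 1 month |
| Row available in Table B-7.1.1 | none (lowest is 15 months) | none (lowest is 15 months) |

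Both women can contribute to the DNG column of the outcome tables, and neither can be placed in the DNG baseline table. In the first example 12/15 = 80% of the qualifying time is on another drug. That figure describes one woman. It is not the contaminated share of the DNG column, because under 5.1 events during the GnRH agonist period are not assigned to DNG.

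**Illustration of size.** Let c be the share of DNG women-years in a long-term table that comes from women with under 15 months of DNG. Let R_late and R_early be the rate ratios after and before 15 months of DNG, against a common reference rate. The ratio seen in the column is

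R_seen = R_late × (1 − c) + R_early × c.

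The documents do not give c. Taking 20-40% as an assumption:

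- Late effect only (R_late = 2, R_early = 1): c = 0.2 gives 1.6 + 0.2 = 1.8; c = 0.4 gives 1.2 + 0.4 = 1.6.
- Early effect only (R_late = 1, R_early = 2): c = 0.2 gives 0.8 + 0.4 = 1.2; c = 0.4 gives 0.6 + 0.8 = 1.4.

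The direction therefore depends on when an effect occurs. This also assumes that women-years are allocated in the same way as events. SAP 5.1 speaks only of outcomes and events, so that is an inference.

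**What else is left open.** The note to Table C-3.4.1 says that rates are based on observation time of 15 months or more. It does not say whether this time is on the column drug, or whether the first 15 months count in the denominator. The SAP does not say which gap ends continuous intake for this flag, or whether use before study entry counts.

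**The case against.** The strongest reply is that Table B-7.1.1 already shows the intended meaning. Its rows start at 15 months of DNG, so its remark "They may have started with other than DNG treatment" fits women with 15 months on DNG whatever drug they began with. The SAP also uses EMT for a single treatment, for example where a switcher is someone coming from another EMT (section 3) and where only the first stop or switch of the EMT prescribed at entry is counted (Table B-8.12.1). On that reading, 6.2.2 already means continuous use of one treatment. This may well be the intention, but neither 6.2.2 nor the C-3.4.1 note says so, and those are the texts that govern the outcome tables.

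The Ex-use column in C-3.4.1 does not settle the matter. A woman who stops after 15 months on one drug would also be an ex-user. The notes to the SAE tables further attribute SAEs within 3 months of stopping to the last treatment used, so current-treatment assignment is not the whole rule there. For a recent switcher the last treatment is still DNG, so the problem remains.

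A reader might infer more than the documents support:

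- **That women with a few weeks of DNG are plainly counted as long-term DNG users throughout.** Table B-7.1.1 contradicts this for the baseline tables.
- **That long-term DNG risk is not measured.** Rates of anemia, depression and SAEs in long-term users are planned. The worded objective on long-term use (SAP section 2) concerns adolescents and also covers other treatments.
- **That no woman can reach 15 months on OAED, so OAED cannot serve as a long-term comparator.** The protocol introduction does say of danazol and GnRH agonists that "treatment for endometriosis with these medications needs to be stopped after 6-12 months". But OAED pools the two, consecutive courses could together exceed 15 months, and add-back therapy is handled as one regimen that ends when the add-back ends (SAP 5.2). No formal long-term comparison is planned either: the Section D comparisons cover the primary outcomes.

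**Conclusion.** The point holds as an inconsistency that leaves listed secondary outcomes open to exposure misclassification. The governing text lets women with short DNG exposure after another treatment into the DNG long-term columns of C-2.5 to C-2.7 and C-3.4, while B-7.1.1 implies 15 months of DNG itself.

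The size cannot be determined from the documents. The 1.8-1.6 in place of 2 rests on an assumed 20-40% share, no early excess and a common reference rate, and serves only to show the order of the effect. If the drug-specific reading was intended, the fault is one of wording and the share is zero. The primary hypotheses, their alpha and their power do not depend on this flag.

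**What to change.** In SAP 6.2.2, define a long-term user as a woman with 15 months or more of continuous use of the same treatment category as the table column, with the clock restarting at a switch between categories. Apply this to B-7, C-2.5 to C-2.7 and C-3.4, and align the notes to Tables B-7.1.1 and C-3.4.1. The same text should state:

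- which gap breaks continuous use (for example the 4 weeks already used for restarters);
- whether the first 15 months enter the denominator, and that women-years follow the same column rule as events;
- whether use before study entry counts;
- whether the clock for OAED and NAED runs on the pooled cohort or on each sub-column, since a change from GnRH agonist to danazol is a switch only at the lower level.

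The work is a short text change and the re-derivation of one flag. The follow-up questionnaire (SAP Appendix II, question 1) already records each medication with start and stop dates. The cost is fewer long-term women-years, probably mainly in OAED, where these columns may be sparse.

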#### 7. Interim Analyses and Data Monitoring

#### 7.1 Data Monitoring

This study will maintain scientific independence and will be governed by an independent Safety Monitoring and Advisory Council (SMAC). Bayer Schering Pharma AG Berlin will provide an unconditional grant. The Berlin Center for Epidemiology and Health Research (ZEG), Germany and its research team will be accountable to SMAC in all scientific matters.

The SMAC members will be international experts in relevant scientific fields (e.g., epidemiology, gynecology, psychiatry and internal medicine). The council is responsible for regular review and evaluation of safety data during study conduct as well as for review and approval of the study protocol, statistical analysis plan, interim results, and final study report.

#### 7.2 Interim Analysis

Biannual interim reports will be provided to the funder following the release of the interim analyses results by the independent Safety Monitoring and Advisory Council.

#### 8. Structure of the Analysis Tables

The analysis will be divided in to four sections: Section A – Population Distribution, Section B – Population Characteristics, Section C – Clinical Outcome, and Section D - Comparisons and Inferential statistics.

Baseline characteristics and follow up-characteristics will be displayed for the AT and ITT population. Clinical outcome will be displayed for the AT population, if not otherwise specified.

